#### End points related to epigenetic clocks

- 1. Influence of intervention on epigenetic age measured by available chronological and biological epigenetic clocks.
- 2. Influence of disease on available epigenetic clocks.
- 3. Predictive power of epigenetic clocks for the outcome of the intervention and disease.
  - a. Epigenetic clock measurements at baseline and
  - b. Epigenetic clock measurements obtained from old bio-banked samples.

## 10.5.4 Secondary analyses

Details on analysis of secondary endpoints (more details will be provided in the statistical analysis plan)

| Variable                | Definition   | Definition 2 | Statistical test   |
|-------------------------|--|--------------|--|
| Blood pressure          | Changes in blood pressure after inclusion (morning day of inclusion vs day 1 + 4 hours, day 3 and day 7).  |              | Wilcoxon signed rank   |
| Blood pressure II       | Standardized blood pressure measured at inclusion and end of study visit.  |              | T test for change from
before study (latest
measurement before
start of disease) and start
of study to end of study
in SBT and DBT in
intervention vs placebo
group |
| Respiration support     | Number of hours on respiration support from first tablet is taken to patient is off all respiration support for at least 12 hours.                     |              | Wilcoxon signed rank   |
| Body temperature        | Number of days with temperature above 38 at any point from inclusion to discharge.   |              | Wilcoxon signed rank   |
| Body temperature        | Number of days with
temperature above 38 at
any point from inclusion
to discharge divided on
number of days from
inclusion to discharge |              | T test for average in intervention vs placebo group.   |
| NEWS score              | Change in NEWS score
from -4 hrs - 0 hrs before
first tablet to 1, 3, 7 days
after first tablet   |              | T test for average in intervention vs placebo group  |
| Quality of life         | EQ 5D (paper version) 2
weeks prior to
admission, on day 1 and
at 90 days   |              | T test for average in intervention vs placebo group  |
| Duration of stay in ICU | Hours after first capsule is taken to transfer to other non-ICU department or home   |              | Wilcoxon signed rank   |
| Number of infections    | Number of newly diagnosed infections   |              | Wilcoxon signed rank   |

|  |   |                                       | 1   |
|--|---|---------------------------------------|---|
|  | from inclusion to end of trial  |                                       |   |
| Number of infections 2   | Number of newly diagnosed infections with identified agent from inclusion to end of trial   |                                       | Wilcoxon signed rank  |
| Changes in hearing (clinical examination, portable audiometer, tympanometer and otoscopy | Changes in hearing thresholds from first week of inclusion compared to 90 days after inclusion.   |                                       |   |
| Antibiotic use   | Days on antibiotics after inclusion to end of trial   |                                       | Wilcoxon signed rank  |
| Antibiotic use 2   | Days from inclusion to first antibiotic free day  |                                       | Wilcoxon signed rank  |
| Highest CRP  | Highest CRP from inclusion to end of trial  |                                       | T test for average in intervention vs placebo group                 |
| Frailty  | 1) 4 meters walking test
and grip strength
measured at inclusion,
day 7, and at 90 days.
2) Clinical Frailty Score 2
weeks prior to admission
and at 90 days. |                                       | T test for average in intervention vs placebo group                 |
| Cognitive function   | Forward and backward recall, trail making test and MOCA at day 7* and 90 and week 65.   |                                       | T test for average in intervention vs placebo group                 |
| NAD+ metabolites   |   |                                       |   |
| Epigenetic age changes   | Horvath GrimAge,
Zhang, two of the most
relevant and newer
algorithms available at
the time of analysis   | end of treatment. Predictive power of | group and vs the
dedicated non-
hospitalized control
group |
| DNA methylation genome wide  Histone modifications                                       | Differentially methylated regions between baseline and end of study visit and between treatment groups See 9.5.4  |                                       | Genome wide significance.   |
| nistone modifications  | 366 3.3.4   |                                       |   |

\*Or on discharge if before day 7, or later if the patient cannot be tested on day 7.

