#### 10.5.3 Other Secondary Endpoints:

Comparing the intervention group with the placebo group with regards to the following:

- 1. Time to normalization of blood pressure and resolution of fever.
- 2. Respirator days after randomization.
- 3. Length of stay from randomization to medically fit for discharge.
- 4. 90 days, one year and very long-term mortality from randomization.
- 5. Measure NAD+ and metabolite levels BEFORE, during and after acute illness in patients using NR and placebo.
- 6. Number of new infections and re-admission during follow-up.
- 7. If significant differences in endpoints are found in the NR and placebo group, we wish to investigate the following:
  - Epigenetic mechanisms of how NR shortens recovery time after acute illness.
  - b. To identify characteristics of the patients that benefits most from NR supplementation after acute illness.
  - c. To identify the optimal NR dose yielding the largest reduction in recovery time.

See also table 3 with secondary endpoints (except variables only collected at baseline)

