- 1. The null hypothesis in Step 1 is not rejected. Decision: No effect of NR for the doses in the study.
- 2. The null hypothesis in Step 2 is not rejected. Decision: The normal dose is the minimum effective dose.
- 3. The null hypothesis in Step 3 is not rejected. Decision: The medium dose is the minimum effective dose.
- 4. The null hypothesis in Step 3 is rejected. Decision: The low dose is the minimum effective dose.

Assumption

The dose response is assumed to be monotone, i.e., the effect of low dose is less than or equal to the effect of medium dose, which is less than or equal to the effect of normal dose. Or, consequently, that the mean length of hospital stay decreases monotonous from placebo (μ_1) to normal dose (μ_4):

 $\mu_1 \ge \mu_2 \ge \mu_3 \ge \mu_4$.

Adaptation to Estimation

Hypothesis testing will only be performed for the primary outcome. For all secondary outcomes, estimation of treatment effect with 95% (two-sided) confidence intervals will be carried out instead of hypothesis testing in each of the three steps described above. The overall statistical approach will be the same; however, the criterion for performing steps 2 and 3 is that the 95% confidence interval from the preceding step does not contain the null effect value.

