New infections is defined as any infection, mild or serious, occurring between the last point of contact to the next i.e. if a patient has an upper airway infection after discharge, but before the 90 day follow up appointment, this will count as one new infection at the 90 day follow up appointment. The outcome will be the number of new infections per patient, which is a discrete numerical variable.

Re-admissions

Re-admissions is defined as number of all-cause hospital admissions, surgical and medical, up until end of study. The outcome will be the number of new admissions per patient, which is a discrete numerical variable.

Other variables of interest

Metabolites

Rise in NR metabolites from inclusion to day 7 (or discharge if discharged prior to day 7) and until day 90.

Table 1: Overview of outcomes to be reported in the main article. Outcomes to be presented in subsequent articles are listed and defined in the protocol but not shown here.

Level	Outcome	Timeframe	Туре
Primary	Length of hospital stay (to medical fit for discharge)	65 weeks	Time to event
Secondary	Change in grip strength	90 days	Continuous (change from baseline)
	Change in grip strength	7 days	Continuous (change from baseline)
	All-cause mortality	-	Time to event
	Number of new infections per patient	65 weeks	Discrete numerical
	Number of re-admissions per patient	65 weeks	Discrete numerical

6 Statistical Analysis Methods

The overall statistical approach is presented in Section 2.4 and involves 1-3 steps of hypothesis testing and/or estimation of treatment effect. In step 1, only the patients in the normal dose group of NR will be used (in addition to the patients in the placebo group); in Step 2, only the patients in the medium dose group will be used; and in step 3, only the patients in the low dose group will be used. This approach will be followed for the primary and all secondary outcomes. The statistical methods for steps 1-3 will be presented for each type of outcome in the following subsections.

As an exploratory analysis, we will also perform an overall vs. placebo analysis, where the low, medium, and normal dose groups are combined and compared with placebo.

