7.3 Vital Signs

Changes in vital signs (including systolic and diastolic blood pressure [mmHg], heart rate [beats per minute], peripheral 02 saturation (%), respiration frequency (numerical value), temperature (in Celsius degrees) and weight [kg]) will be summarized by treatment group and time point during admission.

8 Statistical Software

All statistical analyses will be done in Stata SE version 17 (StataCorp LLC, College Station, TX, USA).

9 References

- Bauer P. Multiple testing in clinical trials. Statistics in Medicine 1991; 10:871-890.
- ICH E9(R1) Addendum on estimands and sensitivity analysis in clinical trials. *International council for harmonisation of technical requirements for pharmaceuticals for human use*; 2019.
- Senn S. Statistical Issues in Drug Development. John Wiley & Sons, 2007.
- Williams DA. A test for differences between treatment means when several dose levels are compared with a zero dose control. *Biometrics* 1971; 27:103-117.

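### The early blood-pressure row in Protocol 10.5.4 names a before-after test with no term for arm, so as written it does not make the NR-versus-placebo comparison set in 10.5.3

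*Protocol*

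**What the plan says.** The table in Protocol 10.5.4 opens with a row for blood pressure, defined as "Changes in blood pressure after inclusion (morning day of inclusion vs day 1 + 4 hours, day 3 and day 7". The test given is "Wilcoxon signed rank". The row names neither an arm nor a comparator.

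Other rows of the table do name one. The next row, Blood pressure II, specifies a t test of intervention against placebo. The NEWS row, also an early change score, reads "T test for average in intervention vs placebo group".

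Protocol 10.5.3 introduces the secondary endpoints with "Comparing the intervention group with the placebo group with regards to the following", and its first item concerns normalization of blood pressure.

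The SAP does not list early blood-pressure change among its outcomes. Its outcome table in Section 5 carries the note "Outcomes to be presented in subsequent articles are listed and defined in the protocol but not shown here". Section 2.4 states "Hypothesis testing will only be performed for the primary outcome" and asks for treatment-effect estimates with 95% confidence intervals for secondary outcomes. Section 7.3 says that changes in vital signs, blood pressure among them, "will be summarized by treatment group and time point during admission".

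**The concern.** A signed-rank test on change scores tests whether the changes are centred on zero in the patients it is applied to. It has no term for treatment. Patients enter this trial once stable and recovering from acute illness, so blood pressure could plausibly move in both arms for reasons unrelated to NR. If the row is followed literally, a change common to both arms produces a small P value that says nothing about NR. The question in 10.5.3 then goes unanswered for this outcome, and a later article could report a before-after change as if it were a treatment effect.

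**Working it through.** **Is it a misnaming?** Eight rows of the 10.5.4 table name the signed-rank test. The first is early blood-pressure change. The other seven are hours of respiratory support, days with fever, time in ICU, two infection counts and two antibiotic measures. Each of those seven has one value per patient. Respiratory support, for example, is "Number of hours on respiration support from first tablet is taken to patient is off all respiration support for at least 12 hours". With no pair, a before-after test has nothing to act on. Under the between-arm heading of 10.5.3, the natural reading is that the rank-sum test was meant throughout. In the seven rows an analyst would notice the problem. In the blood-pressure row the data are paired, so the test runs and returns a P value for the wrong question.

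**How far can the two tests diverge?** The documents give no figure for this row to reproduce. Their only power statement concerns length of stay and is not affected.

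Inputs from the documents:
- 18 patients on placebo, and 10, 10 and 20 on the three NR doses, so 40 on NR in all (Protocol 10.1; SAP 2.3).
- Two-sided 5% level (SAP 3.1).

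Assumptions: normally distributed changes, the same mean change of d SD in both arms, and no NR effect. The documents state neither a blood-pressure SD nor an expected change, so d is shown over a range.

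Simulated proportion of trials with P<0.05 at one time point:

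| NR patients | Signed rank within NR, d = 0.3 | d = 0.5 | d = 0.75 | Rank sum of change, NR v placebo, any d |
|---|---|---|---|---|
| 40 | about 43% | about 85% | about 99.6% | about 5% |
| 20 | about 23% | about 54% | about 87% | about 5% |
| 10 | about 13% | about 28% | about 54% | about 5% |

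At d = 0 the signed-rank test also rejects in about 5%. The test is valid, but for a different null hypothesis.

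Hand check: the signed-rank test has efficiency 3/π relative to the t test for normal data, so its rejection rate is roughly Φ(d√n × √(3/π) − 1.96), with √(3/π) = 0.977.
- n = 40, d = 0.5: 0.5 × 6.325 × 0.977 − 1.96 = 1.13, giving 87%.
- n = 40, d = 0.3: 0.3 × 6.325 × 0.977 − 1.96 = −0.11, giving 46%.
- n = 20, d = 0.5: 0.5 × 4.472 × 0.977 − 1.96 = 0.22, giving 59%.

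These are slightly above the simulated values, as expected from a large-sample formula.

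Run on all 58 patients together, the signed-rank test rejects in about 96% at d = 0.5, and it cannot distinguish the arms at all.

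**The case against.** The strongest reply is that this is a slip in a test name, not a planned uncontrolled analysis. Section 10.5.3 frames the secondary endpoints as a comparison of arms, and the seven unpaired rows show that the authors used the signed-rank name loosely. That is probably right. It changes the diagnosis but not the need for correction.

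A second reply is that the SAP displaces the row. Protocol 10.5 calls itself an outline of the SAP. SAP 2.4 confines testing to the primary outcome, and SAP Section 6 applies the dose-versus-placebo steps to all secondary outcomes. This shows the intended direction. But the method subsections of Section 6 cover only length of stay, grip strength, mortality and two counts, and Section 7.3 is descriptive. Early blood-pressure change is left with the protocol row as its only named method.

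A reader might infer more than the documents support:
- That placebo data are never used for blood pressure. Section 10.5.3, Blood pressure II and SAP 7.3 all involve the placebo group.
- That NR would be declared effective if its own test were significant and placebo's were not. No such rule is stated. It would also not always favour NR: with 10 NR patients against 18 on placebo, the reverse pattern is the more common.
- That an early safety signal is compromised. Safety evaluation is tabular, and vital signs are summarised by treatment group.

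**Conclusion.** The row is wrong as written: the named test does not answer the NR-versus-placebo question, and the SAP provides no substitute for this outcome. A misnamed rank-sum test is the likely explanation.

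The rejection rates illustrate the gap between the two tests under an assumed shared change. They are not estimates of this trial's error rate. The 40-patient figures also pool the doses, which SAP Section 6 treats as exploratory.

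The consequence is limited. The outcome is secondary and absent from the main-article list, and the sample size and primary analysis are unaffected.

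**What to change.** In the first blood-pressure row of Protocol 10.5.4, or in an SAP entry for this outcome, replace the test with a between-arm comparison of change at day 1 + 4 hours, day 3 and day 7. Either of these would do:
- a linear model of blood pressure on arm and pre-dose blood pressure;
- a rank-sum test of the changes.

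Report the NR-placebo difference with a 95% confidence interval at each time point, in line with SAP 2.4. Check the other seven signed-rank rows for the same naming error and correct them together.

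The cost is wording only. The outcome as defined already calls for these measurements in both arms.

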1.2 Trial Objectives

Primary Objective

The primary objective of this study is to assess the efficacy of dietary supplement NR on shortening recovery time after critical illness.

Secondary Objectives

The secondary objectives of this study are:

- To assess the effect of NR on mortality
- To assess NR adverse events
- Other secondary objectives are described in the protocol but will not feature in the main publication

2 Trial Methods

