6.4 Secondary Discrete Numerical Outcomes

The secondary discrete numerical outcomes are number of new infections per patient and number of re-admissions per patient. Both outcomes are measured as a count from 0 to the maximal number of events (new infections or re-admissions). We expect the maximal numbers of events to be at most 10. The analyses will be performed on the FAS.

Statistical Method for Steps 1-3

The mean number of events per patient will be compared between the NR and placebo groups – in each of the three steps – with a two-sample T test with adjustment for unequal variances (Fagerland et al., 2011).

Presentation of Results

The observed number and percentages in each treatment group in each category (0, 1, 2, ..., max number of events) will be presented together with the observed mean values and standard deviations in each treatment group and the estimated treatment difference with a 95% confidence interval.

Missing Data

If a patient has died, we will impute the missing data with the 80th percentile for the variable of interest (based on all patients regardless of treatment group). In cases where the 80th percentile= 0, the maximum number of events will be used.

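### Protocol 10.5.4 names a paired test for seven secondary variables that have no pairs; SAP 6.4 replaces it for one, so six have no usable named method for comparing NR with placebo.

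*Protocol*

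**What the plan says.** The Protocol 10.5.4 table has a column for the statistical test. Eight rows carry the entry "Wilcoxon signed rank": blood pressure, respiration support, body temperature (days above 38), ICU stay, number of infections, number of infections 2 (identified agent), antibiotic use, and antibiotic use 2. Typical definitions are "Hours after first capsule is taken to transfer to other non-ICU department or home" for ICU stay and "Days from inclusion to first antibiotic free day" for antibiotic use 2.

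Seven other rows name a comparison between arms. One is the second body-temperature row, fever days divided by length of stay, where the entry is "T test for average in intervention vs placebo group". It stands directly below the fever-days row that carries the signed-rank entry.

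Protocol 10.5.3 introduces its list of secondary endpoints with "Comparing the intervention group with the placebo group with regards to the following". The list includes resolution of fever, respirator days and new infections. It does not name ICU stay or antibiotic use.

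SAP 6.4 analyses new infections and re-admissions "with a two-sample T test with adjustment for unequal variances". For outcomes outside the main article the SAP points back to the protocol: "Other secondary objectives are described in the protocol but will not feature in the main publication" (SAP 1.2) and "Outcomes to be presented in subsequent articles are listed and defined in the protocol but not shown here" (outcome overview, SAP Section 5). SAP 2.4 restricts hypothesis testing to the primary outcome and gives secondary outcomes estimates with two-sided 95% confidence intervals.

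**The concern.** The Wilcoxon signed-rank test works on within-patient differences, or on one sample against a fixed value. Total ICU hours or days on antibiotics give one number per patient, and a patient on NR has no partner on placebo. The arms are also unequal (SAP 2.3: 18 placebo, and 10, 10 and 20 on NR), so no pairing could be constructed.

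An analyst who follows the table therefore cannot obtain the intended contrast and must choose another method. If that choice is made after unblinding, a reader may fairly ask whether the results influenced it. For outcomes left to later articles, with no SAP section of their own, the protocol entry is the only record of what was planned.

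A secondary gap concerns death. The table gives no value for patients who die, and the SAP's rules for death cover only the outcomes that the SAP analyses.

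**Working it through.** The plan states no power, alpha or sample size for these variables, so there is no figure to reproduce. The check is a count of rows and a comparison of sections.

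**1. Rows of the 10.5.4 table**

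| Group | Rows | Count |
|---|---|---|
| Signed rank named | blood pressure; respiration support; days above 38; ICU stay; infections; infections 2; antibiotic use; antibiotic use 2 | 8 |
| Intervention-versus-placebo t test named | blood pressure II; fever days/stay; NEWS; quality of life; highest CRP; frailty; cognition | 7 |
| Other or no test | hearing; NAD+ metabolites; epigenetic age; DNA methylation; histone modifications | 5 |
| Total | | 20 |

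**2. Which of the eight have a pair?** Only blood pressure, defined as a change within the patient. A signed-rank test can be run there, but it addresses change over time and not NR against placebo. Without a pair: 8 − 1 = 7.

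**3. Which of the seven does the SAP replace?** SAP Section 6 covers length of stay (6.1), grip strength (6.2), all-cause mortality (6.3), and new infections and re-admissions (6.4). Re-admissions has no row in the protocol table. Only number of infections is replaced: 7 − 1 = 6.

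**4. The six that remain**

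| Row | Between-arm aim | Type |
|---|---|---|
| Respiration-support hours | stated in 10.5.3 (respirator days) | duration, ends after 12 hours off support |
| Days above 38 | stated in 10.5.3 (fever) | count |
| ICU hours | inferred from the table's other rows | duration, ends at transfer |
| Infections with identified agent | stated in 10.5.3 (new infections) | count |
| Antibiotic days | inferred from the table's other rows | count |
| Days to first antibiotic-free day | inferred from the table's other rows | duration, ends at first free day |

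**5. Does SAP 2.4 close the gap?** It changes the form of the result from a test to an estimate with a 95% CI. Section 6 carries this out for its listed outcomes but gives no model or estimator for these six.

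**6. Would a two-sample method behave properly?** Assume no treatment effect and Poisson counts with mean 1 per patient (an assumption; the documents give no rate), with 4000 simulated trials. At two-sided 0.05 the rejection rates are:

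| NR v placebo | Rank-sum | Unequal-variance t |
|---|---|---|
| 20 v 18 | 0.044 | 0.048 |
| 10 v 18 | 0.048 | 0.053 |
| 40 v 18 | 0.048 | 0.054 |

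Both are close to 0.05.

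**7. Is a rank-based estimate enough where many patients have zero hours?** Protocol 4.1 recruits from regular wards as well as intensive care, and the SAPS2 row of Table 3 provides for patients never in ICU, so zero ICU hours are to be expected. Assume that 30%, 50% or 70% of patients have 0 hours and that the rest are exponential, 33% shorter on NR (all assumed). The shift estimate (median of all NR-minus-placebo differences) is then exactly 0 in 35%, 81% and 99% of trials at 40 v 18, and in 32%, 76% and 99% at 20 v 18. For such rows a shift estimate alone says little.

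**The case against.** The strongest reply is SAP 2.4. If its rule for all secondary outcomes reaches these six, no signed-rank test is run and no p value arises. That reading is open, because SAP Section 6 also says that its approach is followed for all secondary outcomes. It leaves two things unresolved: the protocol entry is still wrong, and no estimator is named in its place.

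A second reply is that Protocol 10.5 presents itself as an outline of the SAP, that any analyst would recognise a slip for rank-sum, and that these outcomes are outside the main article. This stands as a limit on importance. It does not remove the gap, because the SAP sends the reader back to the protocol for these outcomes.

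A reader might infer something stronger: that the test would be run against zero within an arm and give a small p value whatever NR does. The arithmetic is right. With m non-zero patients and no negative values, the exact two-sided p is 2^(1−m), for example 2^(−9) = 0.002 at m = 10. But no section plans a one-sample test against zero, so these p values do not measure harm in this trial.

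Nor do the documents support rank-sum for every row. SAP 6.4 uses an unequal-variance t test for infections and cites a comparison favouring parametric methods for discrete counts. A different method for the subset with an identified agent would be inconsistent.

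On death, a reader might infer that the plan cuts these durations at death. It does not say so. It says nothing on the point for these rows.

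**Conclusion.** The point holds as an error of wording with a real gap behind it. Of 20 rows, 8 name the test, 7 of those have no pair, 1 is superseded by SAP 6.4, and 6 are left with a named method that cannot compare NR with placebo.

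This rests on two readings. The first is that the six rows are meant to compare arms, which is stated for three and inferred for ICU stay and the two antibiotic rows. The second is that no other document supplies their method. That rank-sum was intended is likely but is also an inference.

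The matter is minor. It touches secondary outcomes reserved for later articles, and the primary analysis, alpha and sample size of 58 do not depend on it. The gap on death is a secondary point: if time were cut at death, an arm with more deaths could look better on these rows.

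**What to change.** Before database lock:

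- In the six rows, replace the signed-rank entry with a two-sample comparison of NR with placebo, reported as a between-group estimate with 95% CI. Follow the dose steps of SAP 2.4 and Section 6 (20 v 18, then 10 v 18, then 10 v 18), with pooled NR (40 v 18) as exploratory.
- For infections with identified agent, use the unequal-variance two-sample method of SAP 6.4, as for all infections.
- For the other five rows, name the two-sample method and its estimator, with rank-sum if a test is kept. For respiration support and ICU stay, add the number and percentage of patients with any hours in each arm.
- Mark the number-of-infections row as superseded by SAP 6.4.
- If the blood-pressure row is meant to compare arms, compare each patient's change between arms.
- As a separate line, extend the composite strategy of SAP 3.3 to these rows by stating the value given to patients who die. The SAP 6.4 imputation rule is a template for the counts; the three durations need a rule of their own.

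The cost is a few lines of SAP text and no new data. Protocol 10.4 allows amendments to the plan until the day of database lock; after that, the change must be described and justified in the Clinical Study Report. Editing the protocol table itself needs Ethics Committee approval under Protocol 11.4, so a SAP addendum is the lighter route.

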| Adverse events                       |                     | 1-7, DC  | Χ  | Χ   | Χ                                      | X                   | X                      |
| Survival assessment                  |                     | 1-7, DC  | Х  | Х   | Х                                      | Х                   | х                      |

(DC: Discharge)

\*\*Selected number of patients only

i] And every 7th day onwards if still hospitalized.

ii] All ICU patients and patients on the following medical wards are screened: Infectious diseases, internal medicine, pulmonary medicine and acute medicine. See also own section on screening.

iii] Antibiotics and vitamin B3 containing drugs only.

iv] Full physical examination of all major organ systems.

v] Blood pressure, pulse, temperature, respiration rate and 02 saturation.

[vi] See table 3 below for details.

Table 3: Overview of scoring forms and other assessment methods  $^{**}$ 

| CLINICAL TEST/scoring systems                                    | TIMING  |
|--|---|
|  |   |
| EQ5D (filled in by investigator in the presence of the           | 2 weeks prior to admission. On day 1 and on day 90.                     |
| patient).  |   |
|  |   |
| MOCA   | Day 7 and 90 and week 65.   |
| Trail making A   | Day 7 and 90 and week 65.   |
| Trail making B   | Day 7 and 90 and week 65.   |
| Forward and Backward Recall.                                     | Day 7 and 90 and week 65.   |
| NEWS (completed by nursing staff as part of standard treatment). | - Baseline morning and afternoon, day 3 and day 7.                      |
|  |   |
|  |   |
|  |   |
| 4 meter walking test   | At baseline, day 7, day 90 and week 65.                                 |
| Clinical Frailty score (filled in by investigator)               | Pre-baseline, baseline, day 7, day 90 and week 65.                      |
| Grip strength  | At baseline, day 7, at discharge, day 90 and week 65.                   |
|  | (and every occation at hospital).                                       |
| RASS (completed by nursing staff as part of standard             | Day 0, 1, 3, 7 and every 7 th day thereafter for the         |
| treatment of sedated patients).                                  | duration of stay in ICU   |
|  |   |
| Charlson comorbidity index (Filled in by investigator)           | Baseline  |

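### EQ-5D, the walking test and the Clinical Frailty Score have no stated baseline adjustment, and NEWS uses a plain change score; a baseline-adjusted analysis would be more precise

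*Protocol*

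**What the plan says.** The table in protocol 10.5.4 gives the EQ-5D, NEWS and Frailty rows the same test: "T test for average in intervention vs placebo group". The Frailty row covers the walking test, grip strength and the Clinical Frailty Score. No covariate is named in any of these rows.

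Pre-treatment values exist for all of them. Table 3 in protocol 6.1 schedules:
- EQ-5D: "2 weeks prior to admission. On day 1 and on day 90"
- Walking test: "At baseline, day 7, day 90 and week 65"
- Clinical Frailty Score: "Pre-baseline, baseline, day 7, day 90 and week 65"

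NEWS differs. Its row defines the outcome as "Change in NEWS score" from the four hours before the first tablet to days 1, 3 and 7, so baseline enters by subtraction.

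The protocol table is an outline, and its introduction says that "more details will be provided in the statistical analysis plan". The SAP does not give those details for these outcomes. Its section 1.2 states: "Other secondary objectives are described in the protocol but will not feature in the main publication". The note to the outcome table in SAP section 5 sends the reader back to the protocol for the definitions. For grip strength, SAP 6.2 specifies a linear mixed model in which baseline is one of three measurements.

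**The concern.** Two things are left open for EQ-5D, the walking test and the Clinical Frailty Score: which quantity is averaged, and whether baseline is adjusted for. The row labelled Blood pressure II has a test column that begins "T test for change from", so the authors could name a change there when they meant one. That suggests raw values in the other rows. The NEWS row points the other way, because it carries the same wording as the three outcomes and the quantity averaged there is a change.

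The arms are small (18, 10, 10 and 20), and the project design section of the protocol expects some unevenness after randomisation in a heterogeneous ICU population. SAP 2.4 reports secondary outcomes by estimates and confidence intervals, not tests, so interval width is what these analyses deliver. The walking test and grip strength share one protocol row and one test, yet only grip strength received a model that includes baseline in the SAP. No reason is given for the difference.

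**Working it through.** **Inputs.** Group sizes come from protocol 10.1 and SAP 2.3: 18 placebo, 20 at the highest dose, 40 on NR pooled. The two-sided 5% level comes from SAP 3.1. The documents state no power, SD or correlation for these outcomes, so there is no figure of the plan's own to reproduce; the stated 80% power concerns the primary endpoint only. The correlation r between baseline and follow-up is assumed to lie between 0.3 and 0.8, with equal SDs at both times.

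**Formulas**, as variance relative to a t test on the follow-up value:
- follow-up value only: 1
- change score: 2(1 − r)
- ANCOVA: 1 − r²
- ANCOVA relative to change score: (1 − r²) / [2(1 − r)] = (1 + r)/2

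| r | Change score | ANCOVA | Cut v follow-up only | ANCOVA / change score | Cut v change score |
|---|---|---|---|---|---|
| 0.3 | 1.40 | 0.91 | 9% | 0.65 | 35% |
| 0.5 | 1.00 | 0.75 | 25% | 0.75 | 25% |
| 0.7 | 0.60 | 0.51 | 49% | 0.85 | 15% |
| 0.8 | 0.40 | 0.36 | 64% | 0.90 | 10% |

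Interval width scales with the square root of the variance. At r = 0.3, √0.91 = 0.95, and at r = 0.8, √0.36 = 0.60. Intervals are therefore 5% to 40% narrower than with follow-up values alone. Against a change score, √0.65 = 0.81 and √0.90 = 0.95, so they are 19% to 5% narrower. Below r = 0.5 a change score is less precise than the follow-up value alone.

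**Detectable difference at 80% power**, in SD units, from the noncentral t with standard error √[v(1/n₀ + 1/n₁)]. For ANCOVA, v = (1 − r²)(1 + 1/(N − 4)) with one degree of freedom fewer, which charges for estimating the slope.

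| Comparison | Follow-up only | ANCOVA r = 0.3 | 0.5 | 0.7 | 0.8 |
|---|---|---|---|---|---|
| 18 v 20 | 0.94 | 0.91 | 0.82 | 0.68 | 0.57 |
| 18 v 40 pooled | 0.81 | 0.78 | 0.71 | 0.58 | 0.49 |

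If changes are averaged instead, the detectable difference for 18 v 20 is 1.11, 0.94, 0.73 and 0.59 SD at the same four correlations. ANCOVA is better on either reading.

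**The case against.** A reader might infer that the plan ignores baseline for all four outcomes. The documents do not support that. NEWS is a change from the pre-dose score, so the only point there is efficiency. For the other three, each definition lists a pre-treatment value beside the follow-up value, and the wording of the test does not settle what is averaged.

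A reader might also treat the protocol table as the final plan. It is labelled an outline, and the SAP already replaced its t test for grip strength. The SAP also confines hypothesis testing to the primary outcome. Against this, the SAP supplies no model for these outcomes, so the table is the only description available.

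The gain may be small. A day 1 or pre-admission value in an acutely ill patient may correlate weakly with day 90, and at r = 0.3 the cut against a follow-up-only test is 9%. The protocol also expects its strict exclusion criteria to make participants more alike.

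Finally, the notes to Table 3 say that ability to complete assessments varies considerably, and they place the walking test fifth in priority. ANCOVA would drop patients with no baseline walk. This objection stands, and the fix has to deal with it.

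**Conclusion.** The point holds as an improvement, not as an error. The analysed quantity and the baseline adjustment are unspecified for EQ-5D, the walking test and the Clinical Frailty Score, and NEWS uses a less efficient change score.

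It would be too strong to conclude that the planned comparisons are invalid or biased. In a randomised trial an unadjusted t test is valid, and chance imbalance widens uncertainty without biasing the test. The primary analysis and the sample size are untouched, and these outcomes are outside the main publication.

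The size rests on the assumed correlation and on equal SDs. It applies to one follow-up time among patients with both measurements. The 9% to 64% cut applies only if raw follow-up values are averaged; if changes are averaged, as they are for NEWS, the cut is 35% to 10%.

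**What to change.** Amend the 10.5.4 table, or add a short section to the SAP, before database lock. Protocol 10.4 permits this.

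- **EQ-5D:** ANCOVA of the day 90 value on treatment, with the day 1 value as covariate.
- **Clinical Frailty Score:** ANCOVA of the day 90 value on treatment, with the pre-admission score as covariate. This is the pair of times that the Frailty row already names.
- **Walking test (inclusion, day 7, day 90) and NEWS (pre-dose, days 1, 3 and 7):** a linear mixed model with baseline among the outcomes, in line with the SAP's grip-strength model. Patients without a baseline walk then stay in.

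One detail matters for the mixed models. The grip-strength model includes a treatment main effect, so the arms may differ at baseline. With complete data, its difference in changes then equals the plain change-score difference. To obtain the ANCOVA gain, leave out the treatment main effect so that the arms share one baseline mean, as randomisation implies.

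Name the covariate for each outcome, because EQ-5D and the Clinical Frailty Score each have more than one pre-treatment value. State a rule for missing baselines, and say how patients who cannot walk at baseline are handled, since the mixed model assumes data missing at random.

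The cost is about one degree of freedom per model and the text of that rule. No new data are needed.
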